#### **7.4 Guidelines for adverse event recording**

**7.4.1** The Common Terminology Criteria for Adverse Events version 4.0 (CTCAE v4.0, [http://evs.nci.nih.gov/ftp1/CTCAE/CTCAE\\_4.03\\_2010-06-14\\_QuickReference\\_5x7.pdf](http://evs.nci.nih.gov/ftp1/CTCAE/CTCAE_4.03_2010-06-14_QuickReference_5x7.pdf)) will be used for grading adverse events

**7.4.2** The investigator must assess the relationship of any AE or SAE to the use of study treatment using the following guidelines outlined in the table below:

Table 7.5.3 ATTRIBUTION OF ADVERSE EVENTS		
Code	Descriptor	Definition
5	Definite	The adverse event is clearly related to the investigational treatment
4	Probable	The adverse event is likely related to the investigational treatment
3	Possible	The adverse event may be related to the investigational treatment

2	Unlikely	The adverse event is doubtfully related to the investigational treatment
1	Unrelated	The adverse event clearly not related to the investigational treatment

### **7.5 Monitoring of adverse events**

Subjects having AE's or SAE's will be monitored with relevant clinical assessments and laboratory tests as determined by the subject's treating physician. All adverse events must be followed to satisfactory resolution or stabilization of the event(s). Any actions taken and follow-up results must be recorded in the subject's medical record. For all AE's or SAE's which require the subject to be discontinued from the study, relevant clinical assessments and laboratory tests will be repeated as clinically indicated, until final resolution or stabilization of the event(s).

### **7.6 Adverse event reporting**

- 7.6.1 Notification of all SAE's must be reported to the Principal Investigator ([name]) or his designee by calling [contact]. A written report should be submitted to the appropriate Institutional Review Board (IRB) and UAB Clinical Trials Monitoring Committee per institutional policy.
- 7.6.2 Adverse events will be reported to the Clinical Trials Monitoring Committee.

### **7.7 Data and safety monitoring plan**

- 7.7.1 This protocol will follow the UAB Data and Safety Monitoring Plan maintained by the UAB Comprehensive Cancer Center.
- 7.7.2 Serious adverse events will be reviewed in the UAB radiation oncology treatment planning or new patient conference and the Department of Radiation Oncology Quality Assurance committees.

### **7.8 Early Termination**

Patients may be discontinued from study prior to completion of study requirements for any of the following reasons:

- 7.8.1 The patient has a clinically significant adverse event as determined by the principal investigator
- 7.8.2 The patient requests to be withdrawn from the study

- 7.8.3 The patient fails to comply with the requirement for study evaluation/visits
- 7.8.4 Other conditions for which, in the investigator's opinion, it is in the patient's best interest to be withdrawn from the study
- 7.8.5 Patient did not meet eligibility requirements

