## **7.3 Adverse Events (AE's) and Serious Adverse Events (SAE's)**

- 7.3.1 Definition of AE: Any untoward medical occurrence, which does not necessarily have a causal relationship with the study

Protocol Version: May 12, 2020

Amendment # 1

Page 15 of 26

treatment. This includes any physical or clinical change experienced by the subject, whether or not considered related to the study treatment. An AE can therefore be any unfavorable or unintended sign (including an abnormal lab finding, for example), symptom, or disease (including the onset of new illness and the exacerbation of pre-existing conditions) temporally associated with the study treatment. Progressive prostate cancer disease is not considered to be an AE. Typical symptoms of radiotherapy treatment including grade  $\leq 3$  urinary or gastrointestinal toxicity will not be considered an AE, though they will be documented in the medical record (section 9.0). AE's will be recorded in the medical record.

**7.3.2 Definition of SAE:** Any event occurring during the study evaluation period that results in any of the following outcomes

- Death
- Inpatient hospitalization
- Bleeding requiring administration of blood products
- Any grade  $\geq 3$  urinary or gastrointestinal toxicity

Note that urinary retention requiring temporary urinary catheter placement is considered a grade 2 toxicity by the CTCAE 4.03

All SAE's must be recorded in the medical record. The onset and end dates, severity, duration, effect on study administration (discontinuation/cancellation, for example), relationship to study treatment, and administration of any drugs or therapies to treat the SAE's will be recorded in the medical record.

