## 8.0 STUDY PARAMETERS

- 8.1** For the purposes of this study, acute toxicity will be defined as event(s) that occur within 90 days of the completion of radiotherapy. Acute toxicity will be determined by both intra-treatment examinations and by scheduled follow-up evaluations after the treatment has completed. Late toxicity will be defined as any toxicity occurring > 90 days after the completion of treatment.
- 8.2** Baseline evaluations of enrolled patients must occur within six weeks of study enrollment
- 8.3** "Day 1" will be defined as the date of the first radiotherapy treatment. "Day 42/Week 5/Month 1" will represent the one month follow-up visit after the completion of the last radiotherapy treatment. Day 1 and Day 43/Week 5/Month 1 evaluations may be done within +/- 7 days of the specified day.
- 8.4** "Month 1, 3, 6, 9, 12, 18, and 24" will be defined as the respective follow up visits after the completion of radiotherapy. Month 3-24 evaluations may be done within +/- 30 days of the specified day.

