### **11.2 Secondary endpoints include clinical toxicity and efficacy assessments.**

- 11.2.1 Clinically assess early toxicity, early efficacy, late toxicity, and quality of life for patients receiving focal prostate SBRT.

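### Section 7.8 lets a patient leave the study after an adverse event without keeping the scheduled assessments, so late toxicity and quality of life may look too favourable

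*Combined protocol and SAP*

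**What the plan says.** Section 7.8 opens with "Patients may be discontinued from study prior to completion of study requirements for any of the following reasons". The reasons include a significant adverse event ("The patient has a clinically significant adverse event as determined by the principal investigator", 7.8.1) and failure to meet eligibility (7.8.5). It does not separate stopping radiotherapy from ending data collection.

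Section 7.5 requires adverse events to be followed until they resolve or stabilise. It then addresses this case: "For all AE's or SAE's which require the subject to be discontinued from the study, relevant clinical assessments and laboratory tests will be repeated". How much is repeated is left to clinical judgement, and the repetition ends once the event has resolved or become stable.

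Section 7.3.1 narrows what counts as an adverse event. Typical radiotherapy symptoms, including grade ≤3 "urinary or gastrointestinal toxicity will not be considered an AE, though they will be documented in the medical record". Section 7.3.2 nevertheless lists grade ≥3 urinary or gastrointestinal toxicity as serious.

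On outcomes, Section 8.1 states: "Late toxicity will be defined as any toxicity occurring > 90 days after the completion of treatment". The secondary endpoint in 11.2.1 is to "Clinically assess early toxicity, early efficacy, late toxicity, and quality of life for patients receiving focal prostate SBRT". Table 8.1 schedules toxicity grading, questionnaires and PSA to Month 24, and a biopsy at Month 12. Section 11.5 plans descriptive statistics with exact binomial intervals. It names no analysis population, denominator or rule for missing assessments.

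**The concern.** Treatment must finish within 17 calendar days, while scheduled evaluation runs to 24 months. Once SBRT is over, discontinuation under 7.8 has no treatment left to stop; it can only end data collection. A patient who leaves within 90 days of finishing radiotherapy leaves before the late-toxicity window opens.

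The reason for leaving also overlaps with the outcome. Section 11.3 defines acute and late toxicity as treatment-related adverse events or serious adverse events, and 7.8.1 makes an adverse event a ground for exit. Missing data that depend on toxicity could make the remaining patients look better than the treated group as a whole. With 10 patients, each one lost is 10% of the sample, and late data not collected cannot be recovered.

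**Working it through.** **Step 1: the plan's own figures.** Exact (Clopper-Pearson) 95% limits for x events in n patients are the 0.025 quantile of Beta(x, n−x+1) and the 0.975 quantile of Beta(x+1, n−x). For 9/10 this gives 0.5550 to 0.9975, width 0.4425. For 10/10 the lower limit is 0.025^(1/10) = 0.6915. Both agree with Section 11.6.

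**Step 2: what survives discontinuation.**

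| Item | Kept after exit under 7.8? |
|---|---|
| The event that led to exit | Yes, under 7.5, until resolved or stable |
| A new late toxicity, or later change in a stabilised one | Not required |
| Scheduled CTCAE grading, AUA/SHIM/EPIC, PSA (Table 8.1) | Not required |
| Month 12 biopsy (Table 8.1) | Not required |

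**Step 3: size for late toxicity.** The documents give no exit rate and no late-toxicity rate, so these are assumed scenarios. Let x of 10 treated patients truly have late toxicity, k leave, and e of those k have an event that nobody sees. If those who leave are also dropped from the denominator, the reported rate is (x − e)/(10 − k).

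| Scenario, true rate 2/10 | Reported | Exact 95% CI |
|---|---|---|
| Nobody leaves | 2/10 = 20.0% | 2.5% to 55.6% |
| k=1, e=1 | 1/9 = 11.1% | 0.3% to 48.3% |
| k=2, e=2 | 0/8 = 0% | 0% to 36.9% |
| k=1, e=0 | 2/9 = 22.2% | 2.8% to 60.0% |
| k=2, e=0 | 2/8 = 25.0% | 3.2% to 65.1% |

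One patient with an unseen event lowers the rate by 20.0 − 11.1 = 8.9 points here. For a true 1/10 the drop is 10.0 points (0/9 = 0%), and for a true 3/10 it is 30.0 − 22.2 = 7.8 points (2/9). The last two rows of the table show the reverse direction.

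**Step 4: a denominator alone is not enough.** If all 10 are kept and unseen events count as none, 2/10 is reported as 1/10 = 10% (k=1, e=1) or 0/10 = 0% (k=2, e=2). Showing the number missing lets the reader bound the rate: 1/10 to 2/10 in the first case, 0/10 to 2/10 in the second.

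**Step 5: biopsy.** Assume 8/10 are truly negative and one patient is lost. The reported rate is 8/9 = 88.9% if his biopsy would have been positive and 7/9 = 77.8% if negative. No section links an adverse event to PSA or biopsy result, so the direction is not determined.

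**The case against.** The strongest reply is that Section 7.5 already protects toxicity. A toxicity that caused the exit and persists past 90 days must still be followed and recorded. This stands: a reader might infer from 7.8 that such patients vanish altogether, and 7.5 contradicts that. It does not cover new late events or the scheduled questionnaires, PSA and biopsy.

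The trigger is also narrow and optional. Exit is permitted, not required, and read literally 7.3.1 keeps ordinary grade 2 urinary or bowel toxicity from counting as an adverse event. This stands too, though 7.3.1 and 7.3.2 conflict at grade 3 and must be reconciled. The result is a risk of bias, not an established one.

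Next, 11.2.1 frames the secondary endpoints for patients who receive focal SBRT, which suggests that patients who leave stay in the denominator. Section 11.5 does not say so. The 1/9 and 0/8 figures therefore rest on an assumed denominator, not on a stated rule.

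Finally, the secondary analyses are descriptive, and the scenario intervals overlap heavily. That limits the consequence, but not the case for an inexpensive repair.

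**Conclusion.** The gap is real and of moderate importance. Sections 7.8 and 7.5 together allow scheduled secondary-endpoint data to be lost for reasons that can depend on toxicity, and Section 11.5 has no safeguard. In the assumed scenarios, one exit with an unseen event lowers the late-toxicity rate by about 8 to 10 percentage points. This requires that the event is new and so not captured under 7.5, and that the patient is dropped from the denominator.

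A favourable shift is plausible for late toxicity and quality of life if patients who leave are more prone to late problems. The documents neither state nor quantify this, and the shift reverses if those patients would have had no event.

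Two stronger readings are not supported. A reader might infer that efficacy will also look too good; for PSA and biopsy the documents support only loss of information of unknown direction. A reader might also infer that feasibility is affected; it is not, because a patient who begins SBRT and does not complete it still counts against the 9 of 10 rule in 11.1.2.

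**What to change.** Leave the clinical decision to stop treatment with the investigator. Add to Section 7.8 that a patient who received at least one fraction and is discontinued for any reason other than withdrawal of consent is asked to continue the data collection already scheduled in Table 8.1 to Month 24. This applies as far as he consents and the treating physician considers each procedure appropriate.

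In Section 11.5, state that toxicity is reported with all patients who received any fraction as the denominator, and that the number with missing late assessments is shown beside each rate.

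The sample size, the primary success rule and the visit schedule do not change. The cost is protocol wording, plus a few visits and procedures, including the Month 12 biopsy, that Table 8.1 already schedules, for patients who would otherwise have left.

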## 8.0 STUDY PARAMETERS

- 8.1** For the purposes of this study, acute toxicity will be defined as event(s) that occur within 90 days of the completion of radiotherapy. Acute toxicity will be determined by both intra-treatment examinations and by scheduled follow-up evaluations after the treatment has completed. Late toxicity will be defined as any toxicity occurring > 90 days after the completion of treatment.
- 8.2** Baseline evaluations of enrolled patients must occur within six weeks of study enrollment
- 8.3** "Day 1" will be defined as the date of the first radiotherapy treatment. "Day 42/Week 5/Month 1" will represent the one month follow-up visit after the completion of the last radiotherapy treatment. Day 1 and Day 43/Week 5/Month 1 evaluations may be done within +/- 7 days of the specified day.
- 8.4** "Month 1, 3, 6, 9, 12, 18, and 24" will be defined as the respective follow up visits after the completion of radiotherapy. Month 3-24 evaluations may be done within +/- 30 days of the specified day.

**Table 8.1 Required evaluations and therapies**

	Baseline	Week 1-2	Week 5/Mo 1	Mo 3, 6, 9, 12, 18, 24
PSA	x+		x	x
H and P**	x^		x^	x^
Karnofsky PS	x		x	x
Platelet count or CBC	x			
Quality of Life Indices/Questionnaires*/**	x	x#, ^	x	x
CTCAE v4.0 Toxicity Grading	x	x	x	x
SBRT		xxxxx		
Prostate Biopsy	x			Month 12

\* AUA Symptom Score, SHIM, and EPIC questionnaire - Appendix

# To be completed on the final day of treatment

^ Medications will be recorded

Protocol Version: May 12, 2020

Amendment # 1

Page 18 of 26

+ PSA value within 3 months of enrollment is acceptable as “baseline”

\*\* Due to COVID-19, these study procedures may be conducted remotely, if necessary.

## **9.0 EVALUATION CRITERIA**

### **9.1 Pretreatment evaluations (baseline)**

- Complete medical history
- Physical examination including digital rectal/prostate examination
- Vital signs including weight
- Karnofsky performance status (Appendix B)
- Prostate MRI (a subset of patients may also have MR spectroscopy).
- Completion of quality of life patient questionnaires and surveys, including an American Urological Association (AUA) symptom score survey, Sexual Health Inventory for Men survey, and an Expanded Prostate Cancer Index Composite (EPIC) questionnaire for bowel, sexual, and urinary quality of life. (Appendix C)
- PSA blood work

To be eligible for enrollment, the patient must meet all inclusion criteria. Results of all baseline or screening evaluations, which assure that all inclusion and exclusion criteria have been satisfied, must be reviewed by the investigator prior to enrollment of each patient. In addition, the patient must be thoroughly informed about all aspects of the study, including the study visit schedule, required evaluations, and all regulatory requirements for informed consent. The written informed consent must be obtained from the patient prior to enrollment. Due to COVID-19, these study procedures may be conducted remotely, if necessary.

### **9.2 Technical feasibility**

For the purposes of this study, technical feasibility encompasses two major components: implementation of the intraurethral radiotransponder motion management technique and treatment planning and treatment delivery of single fraction focal SBRT. Treatment planning includes integration of clinical data (exam, biopsy, and medical imaging) to create targets for radiotherapy treatment. Treatment delivery includes the ability to administer planned radiotherapy dose accurately, including pre-treatment physics quality assurance and accurate patient positioning and image guidance.

### **9.2.1 Intraurethral radiotransponder feasibility**

Feasibility of implementing the intraurethral transponder technique will be determined by

- Successful use of the treatment planning system to anticipate the location of the radiotransponder beacons based on the CT simulation scan anatomy
- Successful placement of the beacon-loaded Foley catheter by the treatment planning team
- Appropriate detection of the beacons by the Calypso detection unit
- Transponder beacons continually monitored without interruption during treatment delivery

### **9.2.2 Treatment planning feasibility**

The treatment planning feasibility will be determined by the ability of the treating physician and involved dosimetrists and physicists to produce a radiotherapy treatment plan that meets the specifications in section 6.3 and 6.4.

## **9.3 Treatment delivery**

9.3.1 All treatment plan dose distributions will be verified by UAB staff physicists and must meet the quality assurance standards set forth by the Department of Radiation Oncology prior to patient SBRT administration. Pre-treatment tissue phantom quality assurance checks will be completed. The phantom will be irradiated with the same plan as the patient including all couch angles and beam projections. A dose plane will be calculated and exported from the treatment planning system and will be compared with the measured dose plane from the one of the above techniques. Dose comparisons will be analyzed using the gamma criteria of 3%/3mm and will be considered valid if 95% of points have gamma values of less than 1.

Once plans have met physics quality assurance parameters, treatment delivery will commence. Clinical treatment delivery feasibility will be determined by the ability of the patient to be set up accurately with confirmation of appropriate geometry on kilovoltage imaging.

## **9.4 Treatment phase**

- 9.4.1 The patient will be evaluated at least once by the treating physician during the time that he is undergoing radiotherapy treatment.
- 9.4.2 On the final day of treatment the patient will complete an AUA symptom score, SHIM, and EPIC questionnaires and the treating physician will give toxicity grades for any toxicity present at the time.

## **9.5 Follow-up**

- 9.5.1 As outlined in section 8.0, follow-up examinations will occur at regularly scheduled intervals, occurring every three months for one year and then every six months at the year one to two interval in order to appropriately monitor acute and late toxicity, quality of life, and PSA response.
- 9.5.2 For each follow up visit, the treating physician will complete an updated medical history and perform a physical examination, evaluate KPS, and grade any toxicity noted. Symptom score surveys and questionnaires will be completed by the patient and PSA lab draws will be performed. Some of these study procedures may be conducted remotely, if necessary.

## **11.0 STATISTICAL CONSIDERATIONS**

### **11.1 Endpoints and measure of success**

- 11.1.1 The primary endpoint of the pilot portion of this study is feasibility of focal treatment using the intra-urethral radiotransponder beacon technique as defined in section 9.2.
- 11.1.2 This pilot study will be considered successful if at least 9 of 10 patients who begin treatment are able to complete treatment using the described technique.

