### 3.0 SCHEMA

- 3.1** Patients who meet the enrollment criteria will be enrolled following the decision to proceed with RT for pathologically proven prostate adenocarcinoma. N=10 patients will be enrolled in the study.
- 3.2** Baseline urinary symptoms, rectal symptoms, sexual function, and global quality of life will be assessed using validated patient-reported questionnaires.
- 3.3** A 3-Tesla pelvic MRI containing an axial T2 sequence will be performed without a rectal coil. The use of IV contrast is at the discretion of the treating physician. If an MRI obtained within 3 months prior to enrollment

is deemed clinically acceptable for treatment purposes by the treating physician then reacquisition is not necessary.

- 3.4** CT simulation will be performed with a Foley catheter in place. Radiopaque dummy seeds will be used to mark the anticipated location of the radiotransponder beacons within the catheter.
- 3.5** Utilizing available clinical data (biopsy, physical exam, MRI/MRS, and CT-simulation) physicians, medical dosimetrists, and physicists will create and approve a treatment plan if all dosimetric and quality assurance measurements are met (see sections 6.3 – 6.5). Prescribed dose will be 8.0 Gy per fraction for a total of 5 fractions.
- 3.6** SBRT will be delivered in 9 to 17 calendar days, with every other day fashion in an outpatient clinic setting with an every-other day fashion treatment schedule (see section 6.8). Intraurethral radiotransponder guidance will be performed for all treatments (see section 6.6.4).
- 3.7** Following completion of treatment, patients will be evaluated with clinical exams, laboratory PSA testing, and quality-of-life questionnaires at regular intervals (1, 3, 6, 9, 12, 18, and 24 months post-radiation)
- 3.8** Post-treatment multiparametric MRI and biopsy 1 year from completion of SBRT.

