#### **11.6 Sample Size**

11.6.1 A total of 10 patients will be enrolled into this feasibility study. The study will be considered successful if at least 9 of 10 patients who begin treatment are able to complete treatment using the described technique. A success rate of 90% in 10 patients will lead to an exact binomial 95% confidence interval of (0.5550, 0.9975). This wide confidence interval (width=0.4425) is expected given our small sample size. If all 10 patients are able to complete treatment, the lower confidence limit of the corresponding exact binomial 95% confidence interval will be 0.6915.

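### The success rule counts only patients who start treatment, so a failure at planning or physics QA, which belongs to the stated endpoint, drops out of the feasibility rate

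*Combined protocol and SAP*

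**What the plan says.** Section 11.1.1 names the primary endpoint as "feasibility of focal treatment using the intra-urethral radiotransponder beacon technique as defined in section 9.2". Section 9.2 treats planning and delivery together as one of two main components of feasibility, and includes pre-treatment physics QA under delivery. Two of its criteria are judged before any fraction is given:

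- 9.2.1, first item: "Successful use of the treatment planning system to anticipate the location of the radiotransponder beacons", using the CT simulation anatomy.
- 9.2.2: the ability of the team to "produce a radiotherapy treatment plan that meets the specifications in section 6.3 and 6.4".

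The success rule in 11.1.2, repeated in 11.6.1, requires that "at least 9 of 10 patients who begin treatment are able to complete treatment using the described technique". The sample size is stated differently: "A total of 10 patients will be enrolled into this feasibility study".

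The order of events is clear. Patients are enrolled once radiotherapy has been decided on (3.1), and simulation and planning follow (3.4, 3.5). Under 3.5 the team will "create and approve a treatment plan if all dosimetric and quality assurance measurements are met". Section 6.5.1 requires QA standards to be met before SBRT is given, and 9.3.1 says: "Once plans have met physics quality assurance parameters, treatment delivery will commence".

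**The concern.** The endpoint and the rule that judges it cover different patients. The endpoint includes what happens at planning and QA. The rule looks only at patients who have already passed both. A patient for whom no acceptable plan can be made, or whose plan fails QA, has failed a named part of the endpoint, yet he is in neither the numerator nor the denominator.

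Two things are at stake. The feasibility rate is biased upward relative to the endpoint as defined. And once fewer than 10 patients start, the rule has no single meaning: nine could be a fixed count or 90% of starters, and non-starters might or might not be replaced. This is the trial's only decision rule, so a reader needs to know which reading was applied.

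**Working it through.** **Inputs.** 10 enrolled (3.1, 11.6.1); threshold of at least 9 of 10 (11.1.2, 11.6.1); exact binomial 95% intervals (11.5.1, 11.6.1). The documents give no planning-failure rate, so the failure counts below are worked examples.

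**Formula.** Two-sided Clopper-Pearson interval for x successes in n: lower limit = 0.025 quantile of Beta(x, n − x + 1); upper limit = 0.975 quantile of Beta(x + 1, n − x). When x = n the lower limit is 0.025^(1/n) and the upper limit is 1.

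**The plan's own figures.** 9/10 gives 0.5550 to 0.9975, width 0.4425. For 10/10, 0.025^(1/10) = 0.6915. Both agree with 11.6.1, so the arithmetic there is right.

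**The two denominators compared.**

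| Case | Starters | Enrolled |
|---|---|---|
| One planning failure, none later | 9/9, lower limit 0.6637 | 9/10, 0.5550 to 0.9975 |
| Two planning failures, none later | 8/8, lower limit 0.6306 | 8/10, 0.4439 to 0.9748 |
| Non-starters replaced (assumption): one planning and one delivery failure | 9/10, 0.5550 to 0.9975 | 9/11 = 0.818, 0.4822 to 0.9772 |
| Non-starters replaced (assumption): two planning failures | 10/10, lower limit 0.6915 | 10/12 = 0.833, 0.5159 to 0.9791 |

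With two planning failures and no replacement, the rate among starters is 100% against 80% of those enrolled, and its lower limit is higher by 0.6306 − 0.4439 = 0.1867.

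**When the verdict changes.**

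- *Fixed count of nine, no replacement.* Nine completers are needed whichever denominator is used. Two planning failures leave at most eight, which fails both ways. The verdict never differs.
- *90% of starters, no replacement.* With nine starters, 9/9 passes and 8/9 = 0.889 fails; 9/10 and 8/10 enrolled give the same answers. With eight starters, 8/8 passes but 8/10 fails, while 7/8 = 0.875 fails both ways. The two denominators therefore disagree only with two or more planning failures and no failure among starters.
- *Replacement until 10 start.* The rule can pass at 9/10 starters although 9/11 enrolled is below 90%.

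**How often two or more planning failures would occur.** For an assumed per-patient failure rate q, independent between patients, P = 1 − (1 − q)^10 − 10q(1 − q)^9. This is 0.016, 0.086, 0.264 and 0.624 for q = 0.02, 0.05, 0.10 and 0.20. If nothing else fails, these are the chances of a pass on the 90%-of-starters reading that the enrolled denominator would not give.

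**The case against.** The strongest reply is that the rule, read literally, is safe. Section 11.6.1 places it directly after the statement that 10 are enrolled and computes its intervals on n = 10. Eight completers are not nine, so two planning failures sink the study on either denominator. This stands for the verdict. It does not stand for the reported rate, because the words of the rule still restrict the count to starters. It also leaves open what the rule means with nine starters.

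Second, nothing describes a patient actually being stopped at planning. A first plan that misses its limits may be reworked, and 6.4 calls its organ limits guidelines. That is fair: the documents do not show that planning failures are likely, and the rates used above are assumptions. But 9.2.2 makes planning a test, and a test whose failures cannot be counted is not part of the result.

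Third, this is a descriptive pilot of 10 patients with no formal comparisons. That limits the consequences, but 11.1.2 is still a pass or fail rule.

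Some stronger readings are tempting and are not supported:

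- *The trial will be declared successful wrongly.* This needs the proportion reading or replacement. Section 10.0 (Patient Registration) was not available for this review and may settle the matter; the stated total of 10 enrolled argues against replacement.
- *Plans with 90 to 95% target coverage escape scoring.* Section 6.3.2.1 lies within the specifications that 9.2.2 refers to and calls such coverage acceptable.
- *Patients with lost tracking would count as successes.* Section 9.2.1 lists "Transponder beacons continually monitored without interruption during treatment delivery", and the technique named in the rule most naturally means that section.
- *Every criterion must hold at every fraction.* The documents do not say so. Requiring it would create a stricter endpoint, on which statisticians could reasonably differ.

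**Conclusion.** The mismatch is on the page and should be corrected. The endpoint includes planning and QA, while the success rule is conditioned on having passed them, so the rate among starters overstates feasibility as defined whenever a patient is stopped beforehand. The worked case is 8/8 against 8/10.

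The effect on the verdict is conditional. There is none with a fixed count of nine and no replacement. A pass below 90% of enrolled patients is possible if the rule is a proportion of starters (two or more planning failures and no later failure) or if non-starters are replaced (for example 9/10 starters, 9/11 enrolled). The available text does not settle which reading applies, and the size of any effect depends on failure rates that the documents do not give. The intervals in 11.6.1 are correct.

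**What to change.** In 11.1.2 and 11.6.1:

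1. Apply the rule of at least 9 of 10 to the 10 enrolled patients.
2. Count as failures those who do not start because no acceptable plan was produced or physics QA was not passed. A patient who starts and does not complete remains a failure, as now.
3. Limit any replacement to non-technical withdrawals before planning (such as those under 7.8.2 or 7.8.5), and state how these are counted if not replaced.
4. Report completion among starters as a secondary proportion with its exact 95% interval.

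The study was activated in January 2018, so the amendment should state whether it was made before feasibility results were known.

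The cost is wording in two sections. The sample size and the stated intervals for 9/10 and 10/10 do not change. The downside is that the reported success rate may be lower.

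Separately, 9.2 describes the treatment as a single fraction, while 3.5 and 6.3.1 give five. These sections must be reconciled, since the number bears on what completing treatment means. Whether tracking is scored per fraction, what counts as an interruption, and how a missed 6.4 guideline is treated are useful clarifications for the investigators, but not part of this change.
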